## **1.0 Background**

Inability of the surgeon to identify or localize the diseased PG can occur in 5 – 10% of cases resulting in failed parathyroidectomies (1, 2). As a result, persistent hyperparathyroidism can occur in these patients resulting in unnecessary repeat surgeries that may be associated with increased morbidity and costs (3, 4). Ultrasound imaging, 99mTechnetium-sestamibi scintigraphy, and computed tomography (CT) have so far demonstrated variable efficacy in preoperative localization of diseased PGs (5, 6) and may not always correlate well with the surgical field of view as observed intraoperatively. Consequently, most surgeons rely on visual identification of PGs during surgery, whereby the accuracy of PG identification is eventually determined by her/his surgical skill and experience (7, 8). When in doubt, a surgeon routinely confirms the identity of PG tissue intraoperatively by sending the specimen for frozen section analysis that typically requires a wait time of 20–30 minutes per sample (9) and has additional costs.

By easily being able to distinguish parathyroid from other tissues intraoperatively, postsurgical complications and associated costs may be reduced. The unique discovery of near infrared autofluorescence (NIRAF) in parathyroid tissues demonstrated that optical modalities that detect NIRAF can be utilized for non-invasive and label-free identification of parathyroid tissues with an accuracy as high as 97%. (10, 11) Since then, several research groups have explored the feasibility of localizing parathyroid glands using NIRAF detection with reasonable success, resulting in FDA clearance for marketing this optical technique (12). In this study, we plan to evaluate whether an FDA-cleared device called 'PTeye' (AiBiomed, Santa Barbara, CA) is beneficial or not, for the surgeon and patient during parathyroid operations. The results of such a study will help us to understand and assess the true impact of optical modalities such as PTeye on (i) improving the quality and efficiency of parathyroid surgeries and (ii) minimizing risk of postsurgical complications and related expenses.

## **2.0 Rationale and Specific Aims**

The goal of this study is to assess whether using PTeye – a NIRAF detection modality – can improve patient outcomes and reduce healthcare associated costs after parathyroid surgeries. The specific aims of this study is to determine if PTeye is beneficial or not for (i) intraoperative identification of parathyroid tissues, (ii) improving efficiency of parathyroid surgeries, and (iii) minimizing risk of postsurgical complications.

By being able to quickly and definitively locate parathyroid glands while in the operating room, the duration of surgical procedure could be further reduced. In addition, the number of frozen section biopsy and associated costs can be minimized. Furthermore, repeat surgeries as a result of missing a diseased parathyroid gland at the time of the initial parathyroidectomy for hyperparathyroidism could potentially be avoided.

## **3.0 Animal Studies and Previous Human Studies**

Modalities that rely on NIRAF detection for label-free parathyroid identification have been successfully validated in several studies (13-16). FDA clearance for marketing this application was recently granted to Fluobeam (a commercially available imaging system) and PTeye (a commercial fiber probe-based system) in 2018 (12). Certain outcome studies have reported that imaging-based systems for NIRAF detection such as the PDE Neo II system was able to reduce the number of frozen sections required during

parathyroid procedures (15). However, other studies have reported that they observed no benefit from imaging-based systems in parathyroid localization (17). In a recent study, Thomas *et al.* demonstrated that a fiber probe-based system – the PTeye – was more sensitive in parathyroid identification compared to the imaging-based system by PDE Neo II (18). To date, there has been no studies that determine the impact of a fiber probe-based system (i.e. PTeye) during parathyroid surgeries in minimizing a number of frozen sections obtained intraoperatively or postsurgical complications.

## 4.0 Inclusion/Exclusion Criteria

Inclusions:

- All adults (i.e.,  $\geq 18$  years old) patients with primary hyperparathyroidism who will be undergoing parathyroid surgery
- All adults (i.e.,  $\geq 18$  years old) patients with persistent primary hyperparathyroidism after having undergone a failed prior parathyroid surgery who will be undergoing repeat parathyroid surgery

Exclusion:

- Children and minors
- Pregnant women
  - Those patients who could potentially will receive preoperative pregnancy testing, as is standard before general anesthesia. Any patients with positive pregnancy test results will not be included in the study.
- Patients with concurrent parathyroid and thyroid disease that require total thyroidectomy
- Patients with secondary or tertiary hyperparathyroidism

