## 5.0 Enrollment/Randomization

The research will be designed as a single center study, where patient recruitment will be conducted by the participating surgeons at University of Michigan (UM). At UM, the initial evaluation will be conducted while the surgeon is evaluating the patients at the Endocrine Surgery Clinics. The final eligibility of each patient for participating in this study will be determined by the participating surgeon in accordance of his/her medical conditions. Following the exclusion criteria, the study will aim to accrue all eligible patients who are going to the OR as part of their standard surgical procedure:

1. On the date of procedure consent at clinic or the date of surgery, patients will be given a paper consent form detailing about the outcome study with PTeye in addition to the consent for the surgical procedure that will be performed.
2. The key study personnel will briefly describe the PTeye and its application to the patient.
3. If the patient is interested in participating, the key study personnel will provide the patient with a paper-based consent form.
4. The key study personnel or the surgeon assigned to the patient will be available to discuss the protocol with the patient (including, risks, benefits, alternatives, etc.). The patient will also be provided with the contact information of the principle investigator should they have any questions.
5. If the patient consents to be part of the study, a scan of their signed consent form will be stored digitally in the patient's medical record.

Prior to surgery, the patient will be assigned a unique ID (e.g. Para\_001). The unique ID will be utilized for randomly allocating the patient to the experimental arm (where the surgeon will use PTeye) or a control arm (where the surgeon will not use PTeye). The allocation will be conducted by the study coordinator using 'Random Allocation Software' (<http://mahmoodsaghaei.tripod.com/Softwares/randalloc.html>).

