## 6.0 Study Procedures

For patients assigned to the study arm, the surgeon will use the PTeye as an intraoperative tool to identify if a suspect tissue is a parathyroid or not, during the parathyroid surgery. The surgeon will first take 5 baseline NIRAF measurements on the thyroid gland (or neck muscle, if thyroid is absent) using the disposable sterile fiber probe that is connected to the PTeye console (see Figure 1), as per device functionality requirements. The subsequent step would involve touching the target tissue in the neck with the fiber optic probe, following which the PTeye will indicate to the surgeon if the tissue is parathyroid or not. Parameters which are displayed on the PTeye console – Baseline values, Detection Intensity, Parathyroid Detection Ratio – will be recorded for each patient enrolled in the study arm. PTeye indicates that a tissue is parathyroid if it displays the 'Parathyroid Detection Ratio' is greater than 1.2. The rest of the surgical procedure will follow according to standard protocol.

For patients assigned to the control arm, the surgeon will not use the PTeye and will proceed with the parathyroid surgery as usual, while relying solely on her/his surgical experience in identifying the parathyroid glands during the operations.

**Figure 1.** A commercial fiber probe-based system (PTeye, AiBiomed) for detecting near infrared autofluorescence (NIRAF) utilized for intraoperative parathyroid gland identification. PTeye consists of 1) the console that has a display and indicates to the surgeon if a tissue is parathyroid or not, 2) a detachable fiber optic probe, and 3) a foot-pedal which is activated by the surgeon for tissue NIRAF measurements.

De-identified information regarding (i) patient demographics, (ii) duration of surgery, (iii) number of frozen section analysis performed, (iv) frozen section and permanent histology reports of all excised tissues, (v) blood calcium levels (before surgery, 5-14 days after

surgery and 6 months after surgery), (vi) parathyroid hormone (PTH) levels (5-14 days after surgery and 6 months after surgery) and (vii) postsurgical complications, if any and history of ER visits or hospitalization or repeat surgeries due to high calcium, will be compiled for all enrolled patients. These parameters would then be compared between the study arm and the control arm to truly gauge the impact or value of a device like PTeye for parathyroid surgeries.

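### Patients with a planned partial thyroid resection are eligible, so thyroid work adds variance, though not bias, to operating time and frozen-section counts

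*Combined protocol and SAP*

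**What the plan says.** Section 4.0 admits adult "patients with primary hyperparathyroidism who will be undergoing parathyroid surgery", and adults having a repeat operation for persistent primary disease. Neither inclusion criterion limits what else may be done at the same operation. The one exclusion on thyroid disease is "Patients with concurrent parathyroid and thyroid disease that require total thyroidectomy". Lobectomy and other partial resections are not mentioned.

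Section 5.0 states that "the study will aim to accrue all eligible patients who are going to the OR as part of their standard surgical procedure". It also states that "The final eligibility of each patient for participating in this study will be determined by the participating surgeon", on the basis of medical condition. Section 7.0 adds only that patients at high anesthetic risk will not be approached. On allocation, section 5.0 says "The unique ID will be utilized for randomly allocating the patient to the experimental arm" or to control. No stratification by concurrent procedure is stated.

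Section 6.0 lists the data collected for every enrolled patient, including "ii) duration of surgery, (iii) number of frozen section analysis performed, (iv) frozen section and permanent histology reports of all excised tissues". It continues: "These parameters would then be compared between the study arm and the control arm to truly gauge the impact or value of a device". Section 2.0 gives the aim that these outcomes serve, "ii) improving efficiency of parathyroid surgeries", and names a shorter operation and fewer frozen sections as the hoped-for gains.

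**The concern.** The plan removes the largest concurrent thyroid operation but not the smaller ones. In a patient who has a lobectomy at the same session, part of the operating time goes on the thyroid, and a frozen section may be sent for thyroid disease. Neither has to do with finding parathyroid tissue, yet as section 6.0 is written both enter the comparison.

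The precision of the comparisons for aim (ii) is at stake. Time and frozen sections that the device cannot change act as noise, and a real effect on either outcome becomes harder to see.

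**Working it through.** The plan gives no expected value, SD or effect for duration or frozen sections, so there is no figure of its own to reproduce. Its one calculation, in section 10.0, concerns glands identified (difference 0.7, SD 1.0) and does not enter here.

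**Step 1: eligibility.** A patient with primary hyperparathyroidism and a planned lobectomy meets the first inclusion criterion in 4.0 and no exclusion. The surgeon's discretion in 5.0 and the anesthetic-risk remark in 7.0 do not concern concurrent thyroid surgery.

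**Step 2: outcomes.** Section 6.0 does not limit duration to the parathyroid part or frozen sections to suspected parathyroid tissue. No section adjusts for thyroid resection.

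**Step 3: direction.** A planned resection is fixed before allocation. Under randomisation the expected share of such patients is the same in both arms, so the expected contribution to the between-arm difference is 0.

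**Step 4: size for duration.** Let a share q of patients have a resection that adds L minutes, independently of a base duration with SD s. Then:

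- variance of duration = s² + q(1 − q)L²
- variance ratio = 1 + q(1 − q)L²/s²
- standard error (SE) of the difference in means = √(variance × 2/n), with n per arm

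Inputs: n = 160/2 = 80, from section 10.0. Assumed, because the documents give none of them: q = 0 to 10%, L = 60 minutes, s = 30 to 40 minutes.

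| q | s (min) | q(1 − q)L² | Variance ratio | SE ratio | SE of difference (min) |
|---|---|---|---|---|---|
| 0% | 30 | 0 | 1.00 | 1.00 | 4.74 |
| 0% | 40 | 0 | 1.00 | 1.00 | 6.32 |
| 5% | 30 | 171 | 1 + 171/900 = 1.19 | 1.09 | 5.17 |
| 5% | 40 | 171 | 1 + 171/1600 = 1.11 | 1.05 | 6.65 |
| 10% | 30 | 324 | 1 + 324/900 = 1.36 | 1.17 | 5.53 |
| 10% | 40 | 324 | 1 + 324/1600 = 1.20 | 1.10 | 6.94 |

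The lobectomy part of the between-arm difference alone has an SD of 60 × √(2 × 0.0475/80) = 2.1 minutes at q = 5% and 60 × √(2 × 0.09/80) = 2.8 minutes at q = 10%. This is the same added variance in minutes, not a second effect. For one surgeon with 40 per arm (section 10.0), these SDs grow by √2 to 2.9 and 4.0 minutes, and the ratios in the table do not change.

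**Step 5: sensitivity.** With wider assumptions (s 20 to 40, L 30 to 60, q 5 to 20%) the variance ratio runs from 1.03 (s = 40, L = 30, q = 5%) to 2.44 (s = 20, L = 60, q = 20%). The result depends almost wholly on inputs that the documents do not supply.

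For frozen sections the documents give neither a mean nor an SD, and no size is calculated.

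**The case against.** The strongest reply has four parts.

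- **Nothing shows that such patients will be enrolled.** Their eligibility is inferred from silence. If the share is near zero, so is the effect. This stands, and it is why the range starts at 0.
- **Broad eligibility is defensible.** The protocol draws a line at total thyroidectomy and wants every eligible patient. A narrower population costs recruitment and applicability. This stands, and it is why an option that keeps these patients is offered.
- **The outcomes could be read more narrowly.** Section 6.0 does not use the words total or all for items (ii) and (iii), and section 1.0 describes frozen section as a way to confirm parathyroid tissue. A parathyroid-only count is a possible reading, but no section defines it, and duration has no such reading at all.
- **Much of the data is already collected.** Histology of all excised tissue would largely show who had thyroid tissue removed. This stands in part: what is missing is an analysis rule, and a record of whether the resection was planned before allocation.

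A reader might go further and infer that thyroid time would be credited to PTeye, or that chance imbalance could move mean duration as much as the device could. The documents support neither. Allocation is random, so there is no systematic shift. No expected time saving is stated; the only device-related time given is that measurements add at most 5 minutes (section 7.0). On the assumptions above, ordinary sampling error is already 4.7 to 6.3 minutes, and a share of 5 to 10% raises it by 0.3 to 0.8 minutes.

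**Conclusion.** The gap holds on the text: patients with a planned partial thyroid resection are eligible, and their thyroid work enters the comparisons for aim (ii) with no rule to separate it or adjust for it. The consequence is lost precision, not bias. With a share of 0 to 10%, 60 added minutes and a base SD of 30 to 40 minutes, the variance of duration rises by 0 to 36% and its standard error by 0 to 17%. All three inputs are assumptions, and the size for frozen sections is unknown.

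It would be wrong to conclude that the trial is too small for this reason. The 160 patients were derived from glands identified, which this point does not touch. This is a minor, inexpensive improvement.

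**What to change.** **Preferred.** In section 4.0, extend the thyroid exclusion to any thyroid resection planned for the same operation, decided and recorded before allocation. The cost is one changed line, a small loss of eligible patients and some applicability.

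**Alternative.** Keep these patients and record planned thyroid resection (yes or no) before allocation. Adjust the duration and frozen-section comparisons for that flag, and add a sensitivity analysis without these patients. The cost is one baseline field and two sentences in section 10.0.

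Under either option, thyroid resections decided during surgery stay in the analysis, because the arm could influence them and removing them would be a post-randomisation exclusion.

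Two other remedies that may suggest themselves are better avoided. Stopping the clock at the end of the parathyroid part does not remove thyroid time when the thyroid is done first or the steps interleave. Asking the surgeon to mark the purpose of each frozen section relies on a judgement made after allocation by someone who knows the arm, and could turn random noise into a difference in classification between arms.

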## 5.0 Enrollment/Randomization

The research will be designed as a single center study, where patient recruitment will be conducted by the participating surgeons at University of Michigan (UM). At UM, the initial evaluation will be conducted while the surgeon is evaluating the patients at the Endocrine Surgery Clinics. The final eligibility of each patient for participating in this study will be determined by the participating surgeon in accordance of his/her medical conditions. Following the exclusion criteria, the study will aim to accrue all eligible patients who are going to the OR as part of their standard surgical procedure:

1. On the date of procedure consent at clinic or the date of surgery, patients will be given a paper consent form detailing about the outcome study with PTeye in addition to the consent for the surgical procedure that will be performed.
2. The key study personnel will briefly describe the PTeye and its application to the patient.
3. If the patient is interested in participating, the key study personnel will provide the patient with a paper-based consent form.
4. The key study personnel or the surgeon assigned to the patient will be available to discuss the protocol with the patient (including, risks, benefits, alternatives, etc.). The patient will also be provided with the contact information of the principle investigator should they have any questions.
5. If the patient consents to be part of the study, a scan of their signed consent form will be stored digitally in the patient's medical record.

Prior to surgery, the patient will be assigned a unique ID (e.g. Para\_001). The unique ID will be utilized for randomly allocating the patient to the experimental arm (where the surgeon will use PTeye) or a control arm (where the surgeon will not use PTeye). The allocation will be conducted by the study coordinator using 'Random Allocation Software' (<http://mahmoodsaghaei.tripod.com/Softwares/randalloc.html>).

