## **10.0 Statistical Considerations**

Benmiloud *et al.* studied the impact of NIRAF-based identification of parathyroid glands which comprised of a group of 93 patients where NIRAF was used by a surgeon for parathyroid identification and a control group of 153 patients where NIRAF was not used (19). Their study reported that mean parathyroid glands identified by surgeon with NIRAF imaging was significantly higher at  $3.1 \pm 0.9$ , while that of same surgeon without NIRAF imaging was  $2.6 \pm 0.1$  ( $p=0.0001$ ). Based on this data (mean difference: 0.5 and standard deviation: 1.0), it was determined that in order to observe a statistically significant difference (i.e. for an expected mean difference: 0.7 and expected standard deviation: 1.0), 33 patients would be required per group (for a 95% powered study). Since this study may involve patient follow-up for data up to 6 months after surgery, we will thus assume an approximate data attrition rate of 20%, thus requiring a recruitment of 40 patients per group. In order to detect a difference among individual surgeons, this will require recruitment of 40 patients per arm, per surgeon. Therefore, a total of 160 patients (study and control arm) should be recruited for this study at this study site.

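### The trial is sized for 40 patients per arm per surgeon, but the plan describes no stratification by surgeon and no mechanism to reach those numbers

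*Combined protocol and SAP*

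**What the plan says.** Section 10.0 (Statistical Considerations) first sizes a single two-arm comparison, "for an expected mean difference: 0.7 and expected standard deviation: 1.0", and concludes that "33 patients would be required per group (for a 95% powered study"). It then allows for loss to follow-up: "we will thus assume an approximate data attrition rate of 20%, thus requiring a recruitment of 40 patients per group". That makes 80 patients in all. The next step enlarges the trial: "In order to detect a difference among individual surgeons, this will require recruitment of 40 patients per arm, per surgeon". From this it concludes that "a total of 160 patients (study and control arm) should be recruited for this study at this study site". The surgeon comparison is the only reason given for going from 80 to 160.

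Section 5.0 (Enrollment/Randomization) is the only account of allocation: "The unique ID will be utilized for randomly allocating the patient to the experimental arm (where the surgeon will use PTeye) or a control arm". A study coordinator carries this out with a named software package. No allocation ratio, block scheme or stratification factor is given. On recruitment, the section says that "the study will aim to accrue all eligible patients who are going to the OR".

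Section 6.0 (Study Procedures) compares the study arm with the control arm and does not mention surgeon in that comparison.

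**The concern.** The sample size rests on a layout of arm by surgeon, and the allocation text does not describe how that layout is to be produced. A single list that ignores surgeon can balance the arms overall and still leave them unbalanced within a surgeon. If recruitment is not held to a fixed number per surgeon, the busier surgeon can also take most of the 160 places. The second 80 patients would then be recruited for a comparison that is underpowered for one of the surgeons. Adding surgeon to the analysis model cannot replace patients who were never recruited.

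The overall comparison has a smaller stake. Section 1.0 (Background) says that the accuracy of gland identification comes down to the surgeon's skill and experience, so the plan itself treats surgeon as prognostic. Balancing surgeon between the arms is therefore worthwhile even if the surgeon-level comparison is set aside.

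**Working it through.** **Inputs from section 10.0.** Difference 0.7, SD 1.0, 33 per group, 20% attrition, 40 per arm per surgeon, total 160.

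**Assumptions.** Two-sided α = 0.05 (not stated); two surgeons, from 160 / (2 × 40) = 2 (not stated); 1:1 allocation (implied by equal groups); surgeon caseload shares (not given, so a range is shown).

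**1. The plan's own figures.** The normal approximation is n = 2(z₀.₉₇₅ + z_power)² × SD² / difference².
- At 80% power: 2 × (1.960 + 0.842)² / 0.49 = 32.04, so 33 per group.
- At 95% power: 2 × (1.960 + 1.645)² / 0.49 = 53.04, so 54 per group.

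The stated 33 therefore matches 80% power, not the stated 95%. That is a separate matter; it is noted here because 80% is the working benchmark below. For attrition, 33 × 1.2 = 39.6, which rounds to the plan's 40. Dividing instead, 33 / 0.8 = 41.25, so 42. With 40 recruited, 40 × 0.8 = 32 are evaluable.

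**2. Benchmark with full cells.** With 32 evaluable per arm for one surgeon, power is Φ(0.7 / √(2/32) − 1.960) = Φ(0.84) = 80.0%. The t-test gives 78.7%.

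**3. Both margins fixed, no strata.** Suppose each surgeon has exactly 80 patients and the list is balanced 80:80 overall. One surgeon's number in the PTeye arm is hypergeometric (160 patients, 80 in the arm, 80 drawn).
- P(exactly 40) = 12.6%. If it is 40 for one surgeon it is 40 for the other.
- P(smaller arm of 36 or fewer) = 26.8%.

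For comparison, simple randomisation of one surgeon's 80 patients gives 8.9% and 43.4%.

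**4. What an uneven split costs.** A 36:44 split has an effective size per arm of 2 × 36 × 44 / 80 = 39.6, against 40.

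| Split within a surgeon | t-test power as recruited | t-test power after 20% attrition |
|---|---|---|
| 40:40 | 87.1% | 78.7% |
| 36:44 | 86.8% | 78.3% |

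The cost is 0.3 to 0.4 points.

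**5. Per-surgeon number not enforced.** Simulation of 160 patients with a list balanced 80:80 overall and each patient falling to a surgeon according to the assumed share. Power is for the worse-off surgeon after 20% attrition (normal approximation).

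| Assumed share | Mean smallest cell | P(all four cells ≥ 40) | Mean power |
|---|---|---|---|
| 50:50 | 35.0 | 0.8% | 77.0% |
| 60:40 | 29.5 | 0.03% | 70.0% |
| 70:30 | 21.7 | 0.00% | 57.4% |

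**6. Strata without a per-surgeon limit.** Perfect balance within surgeon but no limit gives the smaller-volume surgeon 160 × 0.40 / 2 = 32 per arm at 60:40 and 160 × 0.30 / 2 = 24 at 70:30. Power after 20% attrition is 71% and 58%. Strata alone recover about one point; the limit per surgeon does the rest.

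**The case against.** Four points can be made for the plan.

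- **A per-surgeon number is stated.** A reader might infer that the plan has no quota at all. It does not support that: section 10.0 gives a recruitment figure per surgeon, which can be read as a target. What is absent is a mechanism to reach it. The results in step 5 apply only if that figure is not followed. For the same reason it would be wrong to say that the intended cells will almost never occur; if the figure is followed and the arms balance overall, they occur 12.6% of the time.
- **Silence is not proof.** A reader might infer that allocation is unstratified. Section 5.0 does not report the software settings, so the supportable statement is that stratification is not described.
- **Exact cells are a poor measure of harm.** This stands. Step 4 shows that missing 40:40 within a surgeon costs almost nothing when that surgeon still has 80 patients.
- **The surgeon aim is thin.** It rests on one sentence, with no surgeon-level analysis specified, and the documents give no caseloads. This also stands, and it limits confidence. But the same sentence is the sole justification for half the sample, so the layout it calls for should be secured.

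Two further inferences do not hold. Chance imbalance of surgeon between randomised arms is not systematic bias, and adjustment can handle it in the overall comparison. And the plan's 33 evaluable per group cannot be used to measure the allocation shortfall, because full cells of 40 also miss it after 20% attrition (32).

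**Conclusion.** The concern holds in a limited form. The plan requires 40 patients per arm per surgeon, describes no surgeon stratification, states no mechanism to reach that number, and does not state how many surgeons take part. If 80 patients per surgeon are in fact recruited, the cost of not stratifying is under one point of power for a 36:44 split. If the number is not enforced and caseloads differ, the smaller-volume surgeon's comparison falls from about 79–80% power to about 70% at 60:40 or 57% at 70:30.

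These figures assume two surgeons, 1:1 allocation, two-sided α of 0.05, and the plan's own difference, SD and attrition. The caseload shares are illustrative. Confidence is moderate: the gap in the text is clear, but its consequence depends on settings and caseloads that the documents do not report.

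**What to change.** In section 5.0:

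1. State the number of participating surgeons.
2. Use one allocation list per operating surgeon, in permuted blocks of varying size that sum to 80, so that each list ends at 40 per arm.
3. Close a surgeon's enrolment at 80 patients, and reword the accrual sentence to match.

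This gives 40 in each of the four cells by design and balances surgeon between the arms in the overall comparison. The limit matters more than the strata, so the second change should not be made without the third.

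The cost is a second list and a few sentences. The total stays at 160. Accrual may take longer, because the faster surgeon stops at 80 while the other continues. The lists must be in place before allocation starts.
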